#### **5.1.4 First diagnosis date and Symptom(s) onset date imputation**

1. If the first diagnosis or Symptom onset day/ month are missing and the year is non-missing:
  - a. If the year part of the date is equal to the year part of the inform consent date, then the imputed date is set to the year start point (01JANYYYY).
  - b. Otherwise the imputed date is set to the mid-year point (01JULYYYY).
2. If the first diagnosis or Symptom onset day is missing and the month/year are non-missing:
  - a. If the month and year part of date is equal to the month and year part of the inform consent date, then the imputed date is set to the month start point (01MONYYYY).
  - b. Otherwise the imputed date is set to the mid-month point (15MONYYYY).

#### **5.1.5 Other imputations**

For laboratory test values below Lower Level of Quantification (LLQ) or above Upper Level of Quantification (ULQ) will be imputed as LLQ or ULQ value, respectively. The numerical part of the reported result will be treated as the actual LLQ or ULQ. These laboratory values will be displayed in listings using the standard unit with the reported sign (“<” or “>”.)

### **5.2 AEs coding/grading**

Adverse events will be coded according to MedDRA dictionary. The MedDRA version used for reporting the adverse events will be described in a footnote.

### **5.3 Laboratory parameters derivations**

The following criteria will be used to define expanded limits and notable abnormalities of key laboratory tests.

#### **Liver Function and Related Variables**

Alanine transaminase (ALT) (SGPT):  $> 3 \times$  Upper Limit of Normal (ULN)

Aspartate transaminase (AST) (SGOT):  $> 3 \times$  ULN

Total bilirubin:  $> 2 \times$  ULN

Alkaline phosphatase:  $> 2.5 \times$  ULN

#### **Renal Function**

Creatinine (serum):  $> 1.5 \times$  ULN

## **Hematology**

Hemoglobin:  $\geq 2$  g/dl decrease from baseline  
Platelet count: < Lower Limit of Normal (LLN)  
White blood cell count: <  $0.8 \times$  LLN  
Neutrophils: <  $0.9 \times$  LLN  
Eosinophils: >  $1.1 \times$  ULN  
Lymphocytes: >  $1.1 \times$  ULN

## **Urinalysis**

Protein urine dipstick: ++\*  
\* ++ is  $\geq 100$  mg/dl

## **5.4 Statistical models**

### **5.4.1 Analysis of continuous data**

Summary statistics (including N, mean, standard deviation, minimum, lower quartile, median, upper quartile, maximum) will be provided for continuous data by visit and treatment group. If applicable and not otherwise stated, means +/- SE will be plotted. If appropriate, summary statistics will also be derived for absolute and percentage changes from baseline.

#### **5.4.1.1 Mixed Model for Repeated Measures (MMRM)**

A mixed effects regression model will be fitted. The endpoint is continuous and its values at all time points from Week 2 up to Week 52 are included on the left hand side of the model as dependent variables. The covariates included as fixed effects are: treatment group, visit, baseline AN count and the interaction between visit and treatment group. An unstructured covariance structure will be applied. In case of non-convergence, alternative covariance structures will be considered. If additional convergence issues are encountered, then modifications to the model will be considered.

### **5.4.2 Analysis of binary (and categorical) data**

#### **5.4.2.1 Summary statistics for binary and categorical data**

Summary statistics for discrete variables will be presented in contingency tables and will include absolute and relative frequencies. If applicable, confidence intervals will be derived as well based on the score method including continuity correction ([Newcombe 1998](#)):

With  $z$  as  $(1 - \alpha/2)$ -quantile of the standard normal distribution (SAS:  $z = \text{PROBIT}(1 - \alpha/2)$ ),  $n$  as total number of subjects (i.e. number of subjects in the denominator), and  $p$  as estimated crude incidence (number of subjects with event /  $n$ ) it is  $q = 1 - p$ .

Then the lower limit is for  $p > 0$  ( $L = 0$  for  $p = 0$ ):

$$L = \max \left\{ 0, \frac{2np + z^2 - 1 - z \sqrt{z^2 - 2 - \frac{1}{n} + 4p(nq + 1)}}{2(n + z^2)} \right\},$$

and the upper limit is for  $p < 1$  ( $U = 1$  for  $p = 1$ ):

$$U = \min \left\{ 1, \frac{2np + z^2 + 1 + z \sqrt{z^2 + 2 - \frac{1}{n} + 4p(nq - 1)}}{2(n + z^2)} \right\}.$$

Note: if  $L > 100p$  then  $L = 100p$  and if  $U < 100p$  then  $U = 100p$ .

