### 1.1 Study design

This is a multicenter, randomized, double-blind, placebo controlled, parallel group study with two secukinumab dose regimens planned in approximately 541 subjects with moderate to severe hidradenitis suppurativa (HS).

The study consists of: Screening (up to 4 weeks), Treatment Period 1 (16 weeks) and Treatment Period 2 (36 weeks; optionally extended up to 48 weeks in case of pandemic major disruptions). Subjects who prematurely discontinue the study, or who complete the study and do not wish to continue in an optional extension study, will need to complete a post-treatment Follow-Up period (8 weeks).

Subjects will be randomized at a 1:1:0.5:0.5 ratio to one of four treatment arms at the time of randomization (baseline) visit:

- Secukinumab 300 mg every 2 weeks
- Secukinumab 300 mg every 4 weeks
- Placebo to secukinumab 300 mg every 2 weeks
- Placebo to secukinumab 300 mg every 4 weeks

Approximately 180 subjects are planned to be randomized to each of the two secukinumab arms and another approximately 180 subjects are planned to be randomized to the two placebo to secukinumab arms. Randomization will be stratified by region, current antibiotic use and body weight.

Subjects who complete Treatment Period 1 will enter Treatment Period 2. At Week 16, subjects who were randomized to one of the two secukinumab arms will continue on the same dose. Subjects who were randomized to the two placebo to secukinumab arms will start either

[figure not shown]
secukinumab 300 mg every 4 weeks or secukinumab 300 mg every 2 weeks according to their treatment arms definition.

The planned end of Treatment Period 2 visit (EOT 2) will be performed at Week 52. At this visit, the site should call Interactive Response Technology (IRT) after performing the scheduled study assessments to record the completion of the Treatment Period for the subject(s). For subjects rolling over to the optional extension study, Week 52 will be the end of study visit; for subjects continuing to the post-treatment Follow-Up period, the visit at Week 60 will be the end of study visit.

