**Table 2-3 Overview of analyses on some safety endpoints**

Analysis period	AEs & Risk management plans (RMP)	SAEs	AEs by severity	study treatment related AEs, death & other significant AEs	notables (lab/vitals)
Entire study period	• crude incidence • exp.time adjusted incidence	• crude incidence • exp.time adjusted incidence	• crude incidence	• crude incidence	• crude incidence

The crude incidence of treatment emergent adverse events will be summarized by primary System Organ Class (SOC) and Preferred Term (PT). Confidence intervals for the crude rate will be derived using the score method including continuity correction ([Newcombe 1998](#)) as described in [Section 5.4.2.1](#).

Adverse events will be summarized by presenting, for each treatment group, the number and percentage of subjects having at least one AE, having an AE in each primary system organ class and having each individual AE (preferred term). Summaries will also be presented for AEs by severity. If a particular AE “severity” is missing, this variable will be listed as missing and

treated as missing in summaries. If a subject reported more than one adverse event with the same preferred term, the adverse event with the greatest severity will be presented. If a subject reported more than one adverse event within the same primary system organ class, the subject will be counted only once with the greatest severity at the system organ class level, where applicable. AEs by severity will be provided by SOC and AEs by severity and PTs may be provided if required at ad-hoc basis.

The most common adverse events reported ( $\geq z\%$  in any treatment group by SOC and PT) will be presented in descending frequency according to its incidence in Any AIN457 group starting from the most common event. The threshold value  $z$  is set to 2 % but it may be updated following review of the dry run outputs.

Separate summaries will be provided for deaths, serious adverse events, other significant adverse events leading to discontinuation.

For the legal requirements of ClinicalTrials.gov and EudraCT, two required tables on treatment adverse events which are not serious adverse events with an incidence greater than 2% and on treatment serious adverse events and SAE suspected to be related to study treatment will be provided by system organ class and preferred term on the safety set population.

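### The closing note of SAP 5.4.2.1 compares 0-1 scale confidence limits with 100p, so read literally it overwrites every upper limit with at least one event (minor units slip, descriptive intervals only)

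*SAP*

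**What the plan says.** SAP 5.4.2.1 sets out the score interval with continuity correction for binary and categorical summaries. It defines p "as estimated crude incidence (number of subjects with event" divided by n, sets q = 1 - p, and takes z as the (1 - alpha/2) "quantile of the standard normal distribution". L is the larger of 0 and a closed-form expression, with L = 0 when p = 0. U is the smaller of 1 and a closed-form expression, with U = 1 when p = 1. The section ends with: "Note: if $L > 100p$ then $L = 100p$ and if $U < 100p$ then $U = 100p".

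SAP 2.6.1 sends the crude incidence of treatment-emergent adverse events to this section: "Confidence intervals for the crude rate will be derived using the score method including continuity correction". Protocol 12.5.2 names the same interval method for adverse event frequencies and has no such note. SAP 2.13 plans confidence intervals in the figures for HiSCR, AN50, flare and NRS30 rates but does not name a method there.

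**The concern.** The note mixes two scales. p, L and U are proportions, while 100p is a percentage, and nothing between the formulas and the note converts the limits. The term 100p appears four times, consistently, and the formulas above it are intact, so damage from reading the PDF is an unlikely explanation.

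A guard of this kind is meant to keep the interval around the estimate. As worded, its upper half does the reverse: it discards a correct limit and substitutes a number 100 times the estimate. The section is a derivation rule that a programmer, or an independent second programmer, would code from. Followed to the letter, it spoils the upper limits of the crude adverse event tables. Not followed, it leaves an undocumented departure from the SAP.

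**Working it through.** The documents print no numerical interval, so there is no figure of theirs to reproduce. The check codes the rule as given.

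**Inputs**
- p = x/n, q = 1 - p, and the formulas for L and U: SAP 5.4.2.1.
- n = 180 for the examples: SAP 1.1, "Approximately 180 subjects are planned to be randomized to each of the two secukinumab arms".
- alpha: given only as a symbol in this section. Assumed 0.05 two-sided, so z = 1.96 and z² = 3.8415. The conclusion was also tested at 0.20, 0.10, 0.01 and 0.001.

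**Formulas (inside the bounds 0 and 1)**
- L = [2np + z² - 1 - z·sqrt(z² - 2 - 1/n + 4p(nq + 1))] / [2(n + z²)]
- U = [2np + z² + 1 + z·sqrt(z² + 2 - 1/n + 4p(nq - 1))] / [2(n + z²)]

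**One case in full: 9 events in 180**
- p = 0.05, 2np = 18, nq = 171, denominator 2(180 + 3.8415) = 367.683.
- U: the root is sqrt(3.8415 + 2 - 0.0056 + 0.2 × 170) = sqrt(39.836) = 6.312. So U = (18 + 3.8415 + 1 + 1.96 × 6.312)/367.683 = 0.0958.
- L: the root is sqrt(3.8415 - 2 - 0.0056 + 0.2 × 172) = sqrt(36.236) = 6.020. So L = (18 + 3.8415 - 1 - 1.96 × 6.020)/367.683 = 0.0246.
- Solving |p - P| - 1/(2n) = z·sqrt(P(1 - P)/n) for P by root-finding gives the same 0.0246 and 0.0958. The closed forms are therefore right.
- The note: 100p = 5. U = 0.0958 is below 5, so U becomes 5. L = 0.0246 is not above 5, so L stays.

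**Other counts at n = 180, 95%**

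| Events | p | L | U by formula | U after the note |
|---|---|---|---|---|
| 0 | 0 | 0 | 0.0260 | 0.0260 (unchanged) |
| 1 | 0.0056 | 0.0003 | 0.0353 | 0.556 |
| 9 | 0.0500 | 0.0246 | 0.0958 | 5 |
| 54 | 0.3000 | 0.2353 | 0.3734 | 30 |
| 90 | 0.5000 | 0.4250 | 0.5750 | 50 |
| 180 | 1 | 0.9740 | 1 | 100 |

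**All cases, n = 1 to 600.** There are 600 × 601/2 = 180,300 combinations with at least one event.
- U < 100p in all 180,300, at each of the five alpha levels. The largest U/p was 6.45 at alpha = 0.05 and 13.4 at alpha = 0.001, far below the 100 needed to escape the rule.
- L > 100p in none.
- With the guard on the limits' own scale (compare with p), it binds in none.

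**When is the overwritten value impossible?** 100p exceeds 1 exactly when p > 0.01. At n = 180 that means two or more events (2/180 = 0.011); only a single event (1/180 = 0.0056) leaves a value below 1. In a larger denominator more counts stay admissible. Taking n = 541, the planned total, as an upper illustration for a pooled safety group, 1 event moves U from 0.0119 to 0.185, and 4 events from 0.0202 to 0.739.

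**The case against.** The strongest reply is that this is a units slip in a redundant safeguard, not an error in the interval. The limits are correct, and both Protocol 12.5.2 and SAP 2.6.1 name a standard method. If L and U were meant to be in percent by the time the note applies, comparing them with 100p is consistent and changes nothing. Adverse events are reported as percentages, so that is a natural guess at the intent, and an existing macro may already work that way. Limits such as 500% or 3000% would also be seen at once; SAP 2.6.1 mentions a review of dry run outputs, though there for setting the frequency threshold.

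Most of this stands, and it is why the point is minor. What does not go away is that the SAP states no conversion, so the percent reading is inference. The rare-event rows give wrong values that a simple range check would pass, although the same macro would expose itself on the common events.

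A reader might infer that a programmer who rescales only part of the calculation would get a plausible wrong limit. The documents do not support that: multiplying L and U by 100 makes the note harmless, and turning p into a percentage before the formulas would make q = 1 - p negative for any p above 1% and break them visibly.

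**Conclusion.** The note is wrong as written. Read literally, it overwrites the upper limit for every non-zero count and leaves lower limits and zero-event rows alone. The result is impossible when p > 0.01 and wrong but admissible when p is 0.01 or less. The worked values assume a two-sided 95% level and n = 180; the overwriting held at every alpha tried and every n up to 600.

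Two stronger readings should be resisted. One is that the trial's interval method is faulty: the formulas are sound, and only the closing line fails. The other is that trial conclusions are at risk. SAP section 1 places the analyses of the primary and secondary objectives in the Week 16 SAP, and this rule tests no hypothesis. Exposure-adjusted rates use a separate exact Poisson interval (SAP 5.4.3). The reach is descriptive: crude adverse event incidence for certain, and other binary summaries where this interval is applied. Minor severity.

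**What to change.** Delete the note. On a common scale it never binds, so nothing is lost. If a guard is wanted, replace 100p by p in all four places (if L > p set L = p; if U < p set U = p) and say that limits are multiplied by 100 only for display. Then confirm that the macro agrees, for instance by running 1, 9 and 54 events in 180 and checking for upper limits of 3.5%, 9.6% and 37.3%. The cost is one line of SAP text and one macro check; no correctly computed interval changes.

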#### 5.4.2.2 Mixed effects logistic regression model (MELRM)

A mixed effects logistic regression model will be fitted. The endpoint is binary and all time points from week 2 up to week 52 are included on the left hand side of the model as dependent variables. The covariates included as fixed effects are: treatment group, visit, baseline AN count (or NRS for Skin Pain/NRS30) and the interaction between visit and treatment group. An unstructured covariance structure will be applied. In case of non-convergence, alternative covariance structures will be considered. If additional convergence issues are encountered, then modifications to the model will be considered.

#### 5.4.3 Exposure-adjusted incidence rate and $100(1 - \alpha)\%$ confidence interval

It will be assumed that for each of  $n$  subjects in a clinical trial the time  $t_j$  ( $j = 1, \dots, n$ ) to the first occurrence of a certain treatment emergent event is observed, or if the event was not experienced, the (censored) time to the end of the observation period or last dose plus 84 days whichever occur earlier. The sequence of first occurrences of an event will be modeled to follow approximately a Poisson process with constant intensity  $\theta$ . The rate parameter  $\theta$  will be estimated as  $\lambda = D/T$ , where  $T = \sum_{j=1}^n t_j$  and  $D$  is the number of subjects with at least one event. Conditionally on  $T$ , an exact  $100(1 - \alpha)\%$  confidence interval for a Poisson variable with parameter  $\theta T$  and observed value  $D$  can be obtained based on (Garwood, 1936), from which an exact  $100(1 - \alpha)\%$  confidence interval for  $\lambda = D/T$  will be derived as follows (Sahai, 1993; Ulm, 1990):

Lower confidence limit  $L = \frac{0.5\chi_{\alpha/2, 2D}^2}{T}$  for  $D > 0$ , and = 0 otherwise;

Upper confidence limit  $U = \frac{0.5\chi_{1-\alpha/2, 2D+2}^2}{T}$ .

where  $\chi_{\alpha, k}$  is the  $\alpha$ -th quantile of the Chi-square distribution with  $k$  degrees of freedom.

The example below shows how this should be handled for cases where subjects switch treatment. In particular for summarizing ‘Any AIN’ as a group, one should take into consideration the sequence of treatments while calculating exposure time for subjects.

**Table 5-1 Examples for calculating exposure time for incidence rates (IR)**

1st treatment	1st exposure	2nd treatment	2nd exposure	Event days (in terms of study day)	Exposure for IR
Placebo	100 days	150 mg	200 days	50 (1st trt) 110 (10 days into 2nd trt)	Placebo: 50 days (event) 150 mg: 10 days (event) Any AIN: 10 days (event)

## 5.5 Patient reported outcomes

### 5.5.1 Dermatology Life Quality Index (DLQI)

The DLQI is a 10-item general dermatology disability index designed to assess Health-related quality of life in adult subjects with skin diseases (e.g. Hidradenitis Suppurativa). The measure is self-administered and includes six domains of symptoms and feelings, daily activities, leisure, work and school, personal relationships and treatment.

The scoring of each question is as follows:

- Very much: Scored 3
- A lot: Scored 2
- A little: Scored 1
- Not at all: Scored 0
- Not relevant: Scored 0
- Question unanswered: Scored 0
- Question 7 “prevented work or studying”: Scored 3

The DLQI total score will be calculated by summing the score of each question resulting in a maximum of 30 and a minimum of 0. The higher the score, the more Quality of Life is impaired.

Meaning of DLQI Scores:

- 0-1 = no effect at all on subject’s life
- 2-5 = small effect on subject’s life
- 6-10 = moderate effect on subject’s life
- 11-20 = very large effect on subject’s life
- 21-30 = extremely large effect on subject’s life

The DLQI will be analyzed under six headings as follows:

- Symptoms and feelings: questions 1 and 2, score maximum 6
- Daily activities: questions 3 and 4, score maximum 6

- Leisure: questions 5 and 6, score maximum 6
- Work and school: question 7, score maximum 3
- Personal relationships: questions 8 and 9: score maximum 6
- Treatment: question 10, score maximum 3

Interpretation of incorrectly completed questionnaires:

There is a very high success rate of accurate completion of the DLQI. However, sometimes subjects do make mistakes.

1. If one question is left unanswered this is scored 0.
2. If two or more questions are left unanswered the questionnaire will not be scored.
3. If question 7 is answered “yes” this will be scored 3. If question 7 will be answered “no” or “not relevant” but then either “a lot” or “a little” is ticked this will then be scored 2 or 1, respectively.
4. If two or more response options are ticked, the response option with the highest score will be recorded.
5. If there is a response between two tick boxes, the lower of the two score options will be recorded.
6. If one item is missing from a two-item subscale that subscale will not be scored.

Of note, in situations where subjects responded to more questions than what was expected or required, the “most severe” answer was entered into the WriteResult (vendor for PRO data) database. In most cases the Self-Evident Corrections (SECs) were defined correctly, however, the SEC regarding question 7A/7B was not designed to select the “most severe” answer. This was confirmed with Novartis HEOR and communicated to the AIN team.

### **5.5.2 Modified Hidradenitis Suppurativa Score**

Collect lesion counts in all affected anatomic regions:

- Left axilla
- Right axilla
- Left groin
- Right groin
- Left gluteal
- Right gluteal
- Other

For each anatomic region, calculate the regional Sartorius score as follows.

Regional Sartorius Score = Region

$$\begin{aligned} &+ 1 * \text{Total noduli} (=AN \text{ counts}) \\ &+ 6 * \text{Total draining fistulae} \\ &+ \text{Distance} \\ &+ \text{Separate,} \end{aligned}$$

Where

Region =

3, if any lesion count in this anatomic region > 0

0, otherwise

Distance =

0, if no active lesions

1, if longest distance between two relevant lesions or size < 5 cm

3, if longest distance between two relevant lesions or size 5-10 cm

9, if longest distance between two relevant lesions or size > 10 cm

Separate =

0, with separation by normal skin

9, without separation by normal skin

The total Modified Hidradenitis Suppurativa Score would be the sum of all affected regional Hidradenitis Suppurativa Scores.

In case subjects make mistakes leading to missing data in region, total noduli (AN count), total fistulae, distance, or separate, the regional Hidradenitis Suppurativa Score will be set to missing and the same will be done for the total Modified Hidradenitis Suppurativa Score except for the two cases below:

- Total noduli is missing, region, total fistulae, distance, separate is not missing, then noduli will be imputed as 0.
- Total fistulae is missing, region, total noduli, distance, separate is not missing, then fistulae will be imputed as 0.

## 5.6 Rule of exclusion criteria of analysis sets

Table 5-2 presents the rules of exclusion criteria of analysis sets.

**Table 5-2 Subject Classification**

Analysis Set	PD ID that cause subjects to be excluded	Non-PD criteria that cause subjects to be excluded
RAN	INCL01*, M-OTH07	Not randomized/Mis-randomized
FAS	INCL01*, M-OTH07	Not in RAN;
SAF	INCL01*, M-OTH07	Not in RAN; No study drug taken

\* Written informed consent must be obtained before any assessment is performed.

